7.2 Administration

Once investigational drug kit numbers have been assigned to the subject, the vial of investigational drug with the assigned kit number will be removed from the freezer. The contents should be thawed by rotating the vials between the palms of the hands, or by setting the vial at room temperature. Care should be taken to protect the product from light.

Investigational drug should be used for intravitreal injection in the study subject within 1 hour after removing the vial from the freezer.

Study drug preparation should be performed by the designated physician.

Each vial contains enough RBM-007 to inject one subject. Each vial will be used one time only.

Write the subject number on the carton label. After injection, vials should be placed in the plastic bag provided by the sponsor, write the subject number and kit number clearly and robustly using a permanent marker, seal and store the bag in a secure area.

7.3 Investigational drug: RBM-007:

Loading the syringe

- 1. A sterile, single-use 250 μ L syringe with several custom marking including 0.1 mL (100 μ L) will be provided separately for IVT injection of RBM-007. Instructions for filling the syringe are as follows:
- 2. Remove the sterile, single-use 250 µL syringe from the packaging.
- 3. Attach a 19-gauge x 1 ½ inch filter needle to the syringe. RBM-007 is dispensed in a 0.5 mL fill in a 2 mL vial.
- 4. Using sterile technique, carefully draw up approximately 200 μ L of RBM-007 into the syringe. (Sufficiently larger volume than 100 μ L is needed to allow for dead space in syringe and needles prior to IVT injection).
- 5. Remove the 19-gauge x 1½ inch filter needle from the syringe and replace with a 30-gauge x 0.5-inch needle for the IVT injection.
- 6. Ensure that the 30-gauge x 0.5-inch needle is affixed tightly to the syringe.
- 7. Align the top edge of the red O-ring of the plunger with the 100 μ L black mark on the syringe, expelling the excess fluid drawn up.
- 8. Ensure there are no air bubbles within the syringe or the needle hub prior to injection, and prior to expelling the excess fluid drawn up.

8 Safety Measures

Safety measures include the following:

- adverse events recording
- BCVA
- complete ophthalmic exam (consisting of an external examination of the eye, routine screening for eyelid/pupil responsiveness, confrontation visual field, slit-lamp biomicroscopy, dilated fundus exam and IOP measurement)
- vital signs (blood pressure and pulse rate) and general physical examination
- optical coherence tomography (OCT), with OCT-A determination
- Fluorescein angiography
- Fundus autofluorescence

9 Adverse Events

All adverse events throughout the course of the study will be monitored and reported on the adverse event form including seriousness, severity, action taken and relationship to study drug. If adverse events occur, the first concern will be the safety of the study participants. For serious adverse events, the participant will be followed until the event has been resolved or deemed medically stable by the investigator.

If a female of childbearing potential becomes pregnant during the study, the subject will be exited from the study. The investigator will notify the subject's physician that the subject has been treated with RBM-007 and will follow the progress of the pregnancy. The investigator will document the outcome of the pregnancy.

10 Method of Analysis

The analysis of data from the study will be performed when all subjects have either completed the visit at Month 4 or discontinued early from the study. Once all of data through Month 4 have been cleaned, verified, and placed in the database, it will be transferred to the personnel performing the analysis.

10.1 General Data Summaries

Continuous variables will be summarized with means and standard deviations and medians with min and max values and categorical variables with frequencies and percentages. Standard parameters and statistical tests will be performed to evaluate for the primary and secondary end points. Specifically, mean change in the CST, manual determination for the presence of subretinal fluid and intraretinal fluid at month three (and at other time points), change in BCVA between baseline and month three, and the number of anti-VEGF injections needed will be measured. Based on the results of these tests, additional testing, as outlined below, may be performed.

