10.2 Efficacy evaluation

Descriptive statistics will be performed on all subjects with special care taken to carefully analyze the change in OCT-A, OCT determined macular thickness, visual acuity (BCVA), fundus autofluorescence and fluorescein angiography. All subjects randomized (ITT population) will be included in the analysis, and subjects will be grouped according to the number of study treatments received (if less than 3). Safety parameters will be evaluated in the patient population.

11 Study Visit Schedule and Procedures

Please see Table 1 for a schematic of the schedule of visits and procedures. The visit schedule includes 5 scheduled visits: baseline, month 1, 2, 3, and 4.

Baseline visit:

- obtain informed consent and authorization
- collect demographic information and medical and ophthalmic history
- collect information about concomitant medication and procedures
- physical examination
- vital signs (blood pressure and pulse rate)
- Pregnancy Test (if indicated)

Perform the following procedures in both eyes:

• standard BCVA, using ETDRS method following refraction

- complete ophthalmic examination: slit-lamp biomicroscopy, indirect ophthalmoscopy and IOP
- Heidelberg OCT imaging
- Angiovue OCT-A imaging
- dilated fundus photography (Heidelberg)
- fluorescein angiography (Heidelberg)
- autofluorescence fundus photography (Heidelberg)
- confirm eligibility
- perform intravitreal injection in study eye (treat fellow eye as standard of care, as indicated)
- query for adverse evets

Week 2 Safety Assessment Visit

- query for adverse events
- query for medication changes and medical procedures
- if rescue criteria met, treat with anti-VEGF at this visit.

Perform the following procedures in both eyes:

- standard BCVA, using ETDRS method following refraction
- complete ophthalmic examination: slit-lamp biomicroscopy, indirect ophthalmoscopy and IOP
- Heidelberg OCT imaging
- Angiovue OCT-A imaging

Month 1, and 2 visits

- query for adverse events
- query for medication changes and medical procedures
- if rescue criteria met, treat with RBM-007 then, standard of care anti-VEGF at that visit. An anterior chamber paracentesis will be performed at the visit as well for intraocular pressure control. Treatment with RBM-007 may be withheld per investigator discretion.

Perform the following procedures in both eyes:

- standard BCVA, using ETDRS method following refraction

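### Section 10.1 allows unnamed, result-driven tests that 10.2 never outlines, and the 10.2 grouping pools anti-VEGF-rescued eyes into the Month 3 CST change

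*Combined protocol and SAP*

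**What the plan says.** The primary endpoint in the Protocol Summary is change in CST from baseline to Month 3. Up to 5 subjects enter a single-site, open-label study with one treatment and no comparator.

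Section 10.1 opens with summary statistics and then states: "Standard parameters and statistical tests will be performed to evaluate for the primary and secondary end points". The next sentence lists quantities: "Specifically, mean change in the CST, manual determination for the presence of subretinal fluid and intraretinal fluid at month three", followed by change in BCVA, and finally "the number of anti-VEGF injections needed will be measured". The section closes with: "Based on the results of these tests, additional testing, as outlined below, may be performed".

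Section 10.2 is what lies below. It begins "Descriptive statistics will be performed on all subjects with special care taken" and names no test, trigger or order of testing. Its only grouping rule is that "subjects will be grouped according to the number of study treatments received (if less than 3". The cover page says that the statistical plans are within the protocol, so the document points to no other plan.

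On rescue, section 11 says for Week 2: "if rescue criteria met, treat with anti-VEGF at this visit". For Months 1 and 2 it says: "if rescue criteria met, treat with RBM-007 then, standard of care anti-VEGF at that visit", and it lets the investigator withhold RBM-007. The Protocol Summary describes rescue as additional to continued RBM-007. Escapes are counted as a secondary endpoint, and Table 1 records concomitant medications and procedures at every visit.

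**The concern.** There are two problems, and the second matters more.

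1. **Open-ended testing.** Section 10.1 promises tests without naming them, and then makes further testing depend on the results. The outline it refers to is not in 10.2. An analyst who has seen open-label data could pick the test, its sidedness and any follow-up test, and still be within the plan.

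2. **Rescue inside the primary summary.** Anti-VEGF can be given at three visits before the Month 3 measurement. The plan counts rescue but does not link it to a subject's CST. The grouping in 10.2 follows RBM-007 exposure, not rescue. A pre-post change in CST could then be read as an RBM-007 effect when part of it comes from another drug. This applies to a plain mean as much as to a p-value.

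**Working it through.** The plan gives no alpha, sidedness, SD, effect size or sample-size calculation, so there is no figure of its own to reproduce. Inputs from the protocol are n of at most 5, paired change in CST, and rescue at Week 2 and Months 1 and 2. Assumptions are a 0.05 level, normal changes for the t-test, and the rescue effects in step 4.

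**Step 1. What each test can do.** The smallest two-sided exact p-value for paired change (sign or signed-rank) is 2/2^n:
- n=5: 2/32 = 0.0625
- n=4: 2/16 = 0.125

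A two-sided paired t-test gives p<0.05 when |mean|/SD exceeds t(0.975, n−1)/√n:
- n=5: 2.776/2.236 = 1.24
- n=4: 3.182/2 = 1.59

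Example with hypothetical changes of −40, −60, −80, −100 and −120 µm: mean −80, SD 31.6, t = −80/(31.6/√5) = −5.66, p = 0.005. The exact signed-rank p on the same data is 0.0625.

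**Step 2. Does choosing between them inflate error?** At n=5 or n=4 the two-sided exact test never rejects. The rule of rejecting if either test rejects is therefore the same as rejecting if the t-test rejects. Under a normal null that is 5% (4.9% in a simulation of 400,000 studies at n=5).

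**Step 3. When does error inflate?** Only if sidedness is also chosen after the data are seen. At n=5:

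| Tests available to the analyst | Null rejection rate |
|---|---|
| Two-sided t only | 5% |
| Two-sided t or two-sided exact | 5% |
| Two-sided t, or one-sided exact in the observed direction (p = 1/32 = 0.031 when all five agree) | about 7% |
| Two-sided t, or one-sided t in the observed direction | 2 × 5% = 10% |
| All of these | just over 10% |

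At n=4 the one-sided exact minimum is 1/16 = 0.0625, so only the one-sided t adds anything.

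**Step 4. Weight of a rescued eye.** At n=5 each eye carries 1/5 = 20% of the mean. If rescue changes CST in one eye by an assumed 50, 100 or 200 µm, mean change moves by 50/5 = 10, 100/5 = 20 or 200/5 = 40 µm. With two rescued eyes these become 20, 40 and 80 µm.

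**Step 5. Does the 10.2 grouping separate rescue?**

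| Eye | RBM-007 injections | Separated by 10.2? |
|---|---|---|
| Not rescued | 3 | No |
| Rescued, RBM-007 continued | 3 | No, same group as the row above |
| Rescued, one RBM-007 dose withheld | 2 | Yes |
| Not rescued, one dose missed | 2 | Yes, but in the same group as the row above |

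The grouping separates by exposure, and rescued and unrescued eyes can share either group.

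**Step 6. Precision of the escape count.** Exact 95% intervals are 0/5: 0 to 52%; 1/5: 0.5 to 72%; 2/5: 5 to 85%. Counts this small need their intervals beside them.

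**The case against.** The strongest reply is that no inference was meant. Section 10.1 is headed as data summaries. The disputed sentence is followed by a list of things to be measured, and the further testing could mean the OCT-A, autofluorescence and angiography that 10.2 adds. This reading is plausible and cannot be excluded. It does not settle the matter: summaries are already covered by the opening sentence of 10.1, and statistical tests of end points is an odd name for measurements. If description was all that was intended, the fix only makes the text say so.

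A reader might infer more: that because a t-test can reach 0.05 and an exact test cannot, picking between them after the fact produces false positives. Steps 2 and 3 show that it does not. The disagreement in the example shows that the exact test has no power at this size, not that error is inflated. The statement about exact tests also covers paired change only; a binomial test against a benchmark rate could go below 0.05, but the plan states no benchmark.

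A reader might also infer that rescue is hidden. It is not: escapes and anti-VEGF injections are counted, and eyes in which RBM-007 is withheld are grouped apart. What is missing is the link from rescue to each subject's CST. It is fair to say that this is a separate matter from testing, and it is treated as such here.

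Finally, the analysis runs once, after all subjects reach Month 4 or discontinue, and nothing in the protocol turns on a p-value. That stands, and it limits the severity.

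**Conclusion.** The point holds, at minor severity, in two parts. Sections 10.1 and 10.2 do not agree on whether testing is planned, and as written 10.1 allows result-driven inference in an uncontrolled study of at most 5 eyes. The possible error inflation is about 7% to 10% against an assumed 5%, and only if sidedness is left open as well as the test. The documents do not support a claim that free choice between two-sided tests inflates error, nor that a firm inferential plan was intended.

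The more consequential part is that a rescued eye with all three RBM-007 injections is pooled into the Month 3 mean CST change at 20% weight. How far this moves the mean depends on the number of rescues and on the rescue effect, neither of which the documents give; 10 to 40 µm per rescued eye is an assumed range. That the pooling can occur follows from the text alone.

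**What to change.** In section 10.1 delete the sentence "Standard parameters and statistical tests will be performed to evaluate for the primary and secondary end points" and the sentence "Based on the results of these tests, additional testing, as outlined below, may be performed". Keep the list of measured quantities. Insert wording such as:

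> *The analysis is descriptive and exploratory; no hypothesis tests are planned. CST and BCVA will be shown for each subject at every visit, with anti-VEGF rescue marked. Change to Month 3 will be given as mean, median and range, for all subjects and separately by whether rescue was given before Month 3. Escape and fluid-free proportions will be given with exact 95% confidence intervals. Efficacy findings are uncontrolled.*

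A t-based confidence interval for mean change is optional. If shown, label it as precision only: a 95% interval excludes zero exactly when the two-sided t-test gives p<0.05, so it can bring the test back by another route.

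The split by rescue is for transparency. Rescue depends on how the eye is doing, so the unrescued eyes are a selected group and their mean is not a clean drug effect either. The subject-level display should carry the interpretation.

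**Cost.** A wording change and slightly more display work. Visits, data collection, sample size and the rescue rules are unchanged, and concomitant treatment is already recorded at each visit. The downside is that no p-value can be quoted.

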Clinical Hypothesis: RBM-007, as used in previous trials of neovascular AMD, has shown an improvement in vision as well as an improvement in subretinal fibrosis in a cohort of subjects with chronic wet AMD. The mechanism of action of RBM-007 is distinct from that of Anti-VEGF treatments. RBM-007 has a powerful fibroblast growth factor-2 inhibition which serves to reduce both VEGF expression as well as inhibit FGF based neovascular response and fibroblast-proliferation. Having both mechanisms of action active early in the disease process will reduce the development of fibrosis in naïve wet-AMD subjects and potentially provide an improved and sustained visual function and favorable anatomic change.

Structure: Single site, open label study

Duration: 4 months

Study Treatment group:

• RBM-007 treatment at baseline, month 1 and month 2. Safety evaluations at week 2, months 3 and 4.

Randomization: all study subjects will receive study drug and those non-responsive to study drug will be treated with rescue anti-VEGF drug, in addition to continuing RBM-007

Visit Schedule:

There will be 6 scheduled visits during the study. These include baseline (Day 0), week 2, and months 1, 2,3, 4/exit.

Primary endpoint one month after the last RBM-007 injection (month 3)

Study Population Characteristics

Number of subjects: Up to 5 subjects will be enrolled

Condition/Disease: Naïve exudative Age-Related Macular Degeneration with associated visual loss.

Key Inclusion Criteria:

- Aged 50 or older, diagnosed with exudative AMD.
- BCVA 5-73, inclusive, in study eye
- Presence of choroidal neovascularization (CNV) secondary to AMD, in study eye

Key Exclusion Criteria:

- History of major ophthalmic surgery in the past 3 months, and any ophthalmic surgery in study eye in the last 30 days
- History of significant ocular disease other than exudative AMD that many confound results
- Hypersensitivity to components of study medication

Response Measures

Efficacy:

- Change in BCVA from baseline to month 3
- Change in intraretinal and subretinal fluid from baseline to month 3, as measured by CST on Heidelberg OCT
- Change in OCT-angiography in study eye from baseline to month 3
- Number of subjects escaping to standard of care
- Change in measured area of intraretinal/subretinal fibrosis

Safety: adverse events, BCVA, complete ophthalmic examination, physical examination and vital signs.

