The CATT study data demonstrates that it is difficult to achieve anatomic flattening of the macula in patients with neovascular AMD.⁴ After one year of required monthly treatment in both the bevacizumab and ranibizumab groups, approximately 50% of subjects continued to have intraretinal and/or subretinal fluid on optical coherence tomography.⁴ When fluid is present in these structures, retreatment is generally necessary to stabilize vision – and subjects with persistent fluid generally have poorer visual gain. RBM-007 has shown, in a previous clinical trial (see attached SUSHI Study CSR) evidence of bioactivity, reducing macular edema associated with choroidal neovascularization in wet AMD. Additionally, the mechanism of action of RBM-007 is more expansive than that of Anti-VEGF treatment alone as RBM-007, a novel oligonucleotide-based aptamer, has potent anti-FGF2 activity, which leads to reduced VEGF expression.^{5,6} In the rat and mouse models of laser-induced choroidal neovascularization, RBM-007 showed activity after intravitreal injection at doses as low as 5 μg/eye⁷. In the laser-induced choroidal neovascularization fibrosis model in rats, it showed activity after intravitreal injection at doses as low as 15 μg/eye⁷ (see Ribomic Investigator Brochure for RBM-007, 2020).

3 Study Objectives

To determine safety and efficacy of intravitreal injections of RBM-007 in subjects with naïve exudative AMD.

4 Study Design

This study is a single-center, open label, 4-month study, designed to evaluate the safety and treatment efficacy of RBM-007 in patients with intraretinal or subretinal edema due to previously untreated neovascular AMD. Up to 5 subjects will be randomized to receive study medication. Study treatment will be administered by intravitreal injections.

There will be 5 scheduled visits during the study. See table 1.

5 Study Population and Entry Criteria

5.1 Number of Subjects:

5

Study Population Characteristics: If both eyes meet all of the inclusion/exclusion criteria the eye with the worse BCVA at baseline will be selected as the study eye. If both eyes meet all of the

inclusion/exclusion criteria and BCVA values are identical for both eyes, the right eye will be selected as the study eye.

5.2 Inclusion Criteria:

• General Inclusion Criteria:

- 1. Male or female patients, 50 years of age or older at baseline

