- **Note:** Subjects that escape to standard of care will continue to be followed for safety through the four-month study period.

6.2 Escape Medications:

• Subjects that escape to standard of care may receive treatment with medications at the investigator's discretion, which in most cases would be an intravitreal Anti-VEGF drug (Eylea, or another drug as determined by the investigator).

7 Study Treatment

RBM-007 injectable solutions (20 mg/mL) are filled (0.5 mL fill) in 2-mL Type 1 Glass (borosilicate) clear vials, capped with 13 mm Gray Butyl stoppers with B2-40 coating (on top) and FluroTec coating

(on bottom), and sealed. Three single use vials will be placed in a carton, and the labeling will include protocol number, kit number, drug concentration and storage conditions. RBM-007 injectable solutions will be provided by RIBOMIC/Representative and will be stored in an appropriate secure area at the investigational site. RBM-007 vials should be protected from light, stored upright, and kept at -20°C.

7.1 Randomization:

Not applicable for this open-label, single-treatment study.

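### The plan does not stop the person reading fluid from knowing the visit, in an uncontrolled before/after study; masked, shuffled batch reading would reduce expectation bias at small cost

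*Combined protocol and SAP*

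**What the plan says.** Section 1 gives the structure as "Single site, open label study" and the sample size as "Up to 5 subjects will be enrolled". Section 4 repeats "single-center, open label, 4-month study". On randomization, Section 7.1 says "Not applicable for this open-label, single-treatment study". Every subject receives RBM-007 and there is no comparison group.

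Section 10.1 names "manual determination for the presence of subretinal fluid and intraretinal fluid at month three" as one of the measures, and extends it to other time points. The primary endpoint in Section 1 is the change in CST on OCT from baseline to Month 3. Section 1 lists change in intraretinal and subretinal edema as a separate secondary endpoint without a method. The Response Measures in the same section say that the change in this fluid is measured by CST.

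Other image-based measures in Section 1 are subretinal hyper-reflective material (SRHM), PED thickness, the size of OCT-A leakage, and "Change in measured area of intraretinal/subretinal fibrosis". The plan does not say whether these are graded by a person or produced by software.

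No section names a grader, describes masked or central reading, sets a reading order, defines when fluid counts as present, or provides for repeat readings. Section 10 places the analysis after every subject has completed Month 4 or discontinued. Section 6.1 lets findings at a visit, including new fluid outside the fovea, support a decision to escape.

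**The concern.** Whether fluid is present is a judgement, and some scans will be borderline. In a randomized comparison with a masked reader, a tendency to read optimistically affects both arms and largely cancels. Here the estimated effect is the Month 3 reading set against the baseline reading of the same eye. A reader who knows that a scan follows three injections, and expects less fluid, adds that expectation to the effect, and no control removes it. The clinical hypothesis in Section 1 states the expectation of anatomic improvement.

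In this design the contrast is visit order, so visit order is what needs masking. There is no treatment comparison to mask. At stake is the credibility of the fluid result, and of any other image measure that turns out to be graded by eye.

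**Working it through.** The plan gives no power calculation, effect size or reading-error rate, so there is no figure of its own to reproduce. Three checks are possible.

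**1. Weight of one reading.** Input: n = 5 subjects, one study eye each (Sections 1 and 5.1). One changed reading moves the proportion by 1/5 = 20 percentage points. For scale, the exact (Clopper-Pearson) 95% interval runs from the 2.5% point of Beta(x, n − x + 1) to the 97.5% point of Beta(x + 1, n − x):

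- x = 2: 40%, interval 5.3% to 85.3%
- x = 3: 60%, interval 14.7% to 94.7%

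One misreading therefore shows in the point estimate but is small beside the sampling uncertainty. The interval covers random error only. It makes no allowance for readings that err in one direction.

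**2. Chance of at least one false dry reading (illustration).** Assumptions, none from the documents: all 5 eyes truly have fluid at Month 3, and a reader who knows the visit independently calls each scan dry with probability b. Then P(at least one) = 1 − (1 − b)^5. The last column assumes that masking halves b.

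| b | 1 − (1 − b)^5 | with b halved |
|---|---|---|
| 0.05 | 23% | 12% |
| 0.10 | 41% | 23% |
| 0.20 | 67% | 41% |
| 0.30 | 83% | 56% |

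The probability reaches zero only if masking removes the bias entirely. The actual reduction cannot be computed from the plan.

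**3. Workload.** Table 1 marks OCT and OCT-A in all six visit columns.

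- OCT, baseline and Month 3 only: 5 × 2 = 10 study-eye volumes
- OCT, all visits: 5 × 6 = 30
- OCT and OCT-A, all visits: 30 + 30 = 60

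Section 1 says "There will be 6 scheduled visits during the study", while Sections 4 and 11 count five. With five visits, the OCT figure would be 5 × 5 = 25. Six is used here because Table 1 and the Week 2 procedures in Section 11 include OCT. Both eyes are imaged, but only study eyes need this reading. The imaging method for fibrosis is not stated, so its workload cannot be counted.

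**Timing.** Analysis waits for the last Month 4 visit or discontinuation, so one batch fits between that visit and the point at which the data are declared clean. No visit or scan is added.

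**The case against.** The strongest reply is that this treats silence as a plan. Open label describes treatment, and Section 10.1 says only that the determination is manual. A reader might infer that the protocol has the grader work with visit labels in view. It does not say so; the supportable statement is that nothing prevents it. A reader might also infer that every image measure is a human judgement. Only fluid presence is called manual; PED thickness, OCT-A size and fibrosis area could be software output. Both corrections stand and limit the point.

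Second, masking may work poorly here. If the grader is the treating investigator, that person may have seen each scan at the visit and may remember the course of one of five eyes. Section 4 describes untreated patients with edema, so a plainly dry scan would be taken as post-baseline. This stands in part. The gain lies mainly with borderline scans, which are the ones that expectation can tip. Recognising an eye does not by itself reveal the visit.

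Third, no grader is named, so the claim that no extra person is needed cannot be checked. No second grader is required, but someone other than the grader must relabel the files and hold the key.

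Fourth, the study is small and largely descriptive, states no decision rule, and has CST as its primary endpoint. That stands as a reason to call this an improvement rather than an error.

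**Conclusion.** The point holds as an inexpensive improvement to a secondary measure. The plan leaves manual fluid reading open to reader expectation in a design whose only contrast is before versus after, and a practical safeguard fits its timetable.

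The 20 percentage points per eye are the sensitivity of a proportion at n = 5. A reader might take them as the size of the bias, but any single changed reading has this effect, including random error that masking does not remove. The probabilities in the working rest on assumed values of b.

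A reader might also infer that the primary result is compromised. The documents do not support that: the primary endpoint is CST, and the plan does not say whether its segmentation is corrected by hand. Escape decisions need readings at the visit, so the number of escapes and of anti-VEGF injections stays unmasked under any version of this proposal.

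Masked reading also does not repair an undefined endpoint. Section 1 (fluid change by CST) and Section 10.1 (manual presence of fluid) must be reconciled in the same edit.

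**What to change.** Add to Section 10.1 text to this effect:

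> For the manual fluid endpoint, and for any SRHM, PED, OCT-A or fibrosis measure graded by a person rather than output by software, study-eye images from baseline and post-baseline visits are exported without date or visit label and shuffled by a site staff member other than the grader, who holds the key. They are graded in one batch by the person who would otherwise have graded them, after the last visit and before the data are declared clean. These readings are analysed. Readings made at the visits continue to serve escape decisions and are filed separately.

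In the same edit, name the grader's role, define when fluid counts as present, say which image measures are graded by hand, and state whether the fluid endpoint is CST, manual presence, or both as separate measures.

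Cost, as a judgement: a few hours of existing staff time for 10 to 30 OCT volumes, and more for about 60 images if OCT-A is graded by hand. Two sets of readings must be filed and may disagree. Masking will be incomplete if the grader is the treating investigator or the change is obvious, and the report should say so.

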All adverse events and serious adverse events will be continually assessed throughout the study. The investigator will assess safety throughout the study to determine appropriateness of continuing dosing and enrollment.

General Statistical methods and Types of Analyses:

The primary efficacy endpoint is:

• Change in edema from baseline to month 3 (one month after the last injection) as measured by CST on Heidelberg OCT

Secondary endpoints include the following:

- Change in BCVA from baseline to month 3
- Change in intraretinal and subretinal edema from baseline to month 3
- CNV lesions components: subretinal hyper-reflective material (SRHM), PED thickness
- Number of subjects escaping to standard of care treatment
- Change in size of OCT-angiography leakage from baseline to month 3

2 Background and Clinical Rationale

Age-related macular degeneration (AMD) is the leading cause of severe vision loss in people over the age of 65 in the United States.¹ The majority of severe vision loss due to advanced AMD is related to the onset of choroidal neovascularization (CNV).^{2,3} Neovascular AMD is characterized by the growth of choroidal vessels into the subretinal space. These vessels have a tendency to leak fluid and blood, causing retinal edema and central vision loss.

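### The only measure in Section 10 specific to fluid type is a present/absent reading, so partial clearing or worsening of subretinal or intraretinal fluid goes unrecorded in that secondary endpoint (minor)

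*Combined protocol and SAP*

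**What the plan says.** Three places describe the fluid outcome, and they do not match.

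- **Section 1, Response Measures (Efficacy):** "Change in intraretinal and subretinal fluid from baseline to month 3, as measured by CST on Heidelberg OCT". Here fluid is measured by CST.
- **Section 1, General Statistical methods:** the primary endpoint is "Change in edema from baseline to month 3 (one month after the last injection) as measured by CST on Heidelberg OCT". A separate secondary endpoint is "Change in intraretinal and subretinal edema from baseline to month 3", with no metric. Another secondary item is "CNV lesions components: subretinal hyper-reflective material (SRHM), PED thickness", so the plan does treat lesion components individually.
- **Section 10.1:** the specific analyses open with CST, and the next item is "manual determination for the presence of subretinal fluid and intraretinal fluid at month three (and at other time points". CST is analysed as a mean change. The two fluid types are read by hand for presence.

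Section 10.2 is descriptive and adds OCT macular thickness, but nothing by fluid type. Section 10.1 mentions statistical tests without naming a test, a significance level or sidedness. No section gives an SD, a power target or a responder rule. On size, "Up to 5 subjects will be enrolled".

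**The concern.** The secondary endpoint is worded as a change in two kinds of fluid, but the analysis section offers only a yes/no reading for each. Change on that scale is visible only when fluid disappears completely or appears where there was none.

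The protocol's own background suggests that residual fluid is common under treatment: after a year of required monthly anti-VEGF injections, "approximately 50% of subjects continued to have intraretinal and/or subretinal fluid on optical coherence tomography". Month 3 here follows three injections of a different drug. That figure is therefore not a forecast for RBM-007, but it does suggest that complete drying is a demanding cut.

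CST does not fill the gap. It is one central thickness, so it cannot attribute a change to subretinal or intraretinal fluid, or separate either from SRHM or PED. It may also not move with fluid outside the center, which the escape criteria in Section 6.1 treat as relevant. At stake is what the trial can report about each fluid type, per eye, at Month 3.

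**Working it through.** The plan states no power, alpha or SD, so there is no figure of its own to reproduce. The check has four steps.

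**1. What each scale records.** Fluid of one type in one eye, with baseline set to 1:

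| Month 3 | Graded change | Presence reading |
|---|---|---|
| 0 | −100% | present → absent |
| 0.10 | −90% | present → present |
| 1.0 | 0% | present → present |
| 2.0 | +100% | present → present |

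The last three rows cannot be told apart on the presence scale.

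**2. How many eyes this could affect.** This rests on assumptions, because the documents give no distribution. Let the fractional fall be normal with mean μ and SD s, capped at full resolution, with 50% of eyes drying. Then P(fall ≥ 1) = 0.5 gives μ = 1.

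- Fall of at least half, but incomplete: 0.5 − Φ(−0.5/s)
- Increase in fluid: Φ(−1/s)

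| s | Large partial fall recorded as unchanged | Increase recorded as unchanged |
|---|---|---|
| 0.5 | 0.5 − 0.159 = 0.34 | 0.02 |
| 1.0 | 0.5 − 0.309 = 0.19 | 0.16 |
| 1.5 | 0.5 − 0.369 = 0.13 | 0.25 |

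With 5 eyes that all have the fluid type at baseline, this is on average 5 × 0.13 = 0.65 to 5 × 0.34 = 1.7 eyes with an unrecorded large fall. It is 5 × 0.02 = 0.1 to 5 × 0.25 = 1.25 eyes with an unrecorded increase.

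**3. Resolution at n = 5.** The best possible binary result is 5 of 5 eyes going from present to absent. The exact two-sided p is 2 × 0.5⁵ = 0.0625 (one-sided 0.031), and the exact 95% interval for the drying rate is 47.8% to 100%. For comparison, a one-sample t test on a continuous change (two-sided 0.05, an assumed level) has power 0.14, 0.40, 0.71 and 0.91 for a mean change of 0.5, 1.0, 1.5 and 2.0 SD.

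**4. Whether the graded scale always gains power.** It does not. Take 30% drying and s = 1.5 in the model of step 2:

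- z = 0.524 cuts off the upper 30%, so μ = 1 − 1.5 × 0.524 = 0.21.
- The cap removes s[φ(z) − z × 0.30] = 1.5 × (0.348 − 0.157) = 0.29.
- The mean fall is 0.21 − 0.29 ≈ −0.07, a 7% worsening.

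Simulated power there is about 7% to 8%, and most of it comes from rejections in the direction opposite to the true mean. At 50% drying, simulated power is about 0.94, 0.50 and 0.28 for s = 0.5, 1.0 and 1.5. The comparison is therefore driven by an SD that nobody has stated.

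**The case against.** The strongest reply is that the plan already has a continuous fluid measure. Section 10.1 puts mean change in CST in the same sentence as the presence reading, the Response Measures tie intraretinal and subretinal fluid to CST, and Section 10.2 adds macular thickness. A partial reduction in central fluid would generally show there, and some worsening would also surface through the escape criteria and the count of escapes. This stands. A reader might infer that the plan reduces its fluid outcome as a whole to present/absent, but the documents do not support that.

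A reader might also infer that an eye with residual fluid counts as a treatment failure. No section defines a fluid responder. Section 10.1 says only that presence will be determined.

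The list in 10.1 is not exhaustive: SRHM and PED thickness are secondary endpoints and are missing from it too. A graded fluid analysis is therefore not ruled out. It is simply not specified, although 10.1 introduces its list as the specific content of the analysis.

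Finally, with at most 5 eyes and mainly descriptive reporting, power at two-sided 0.05 is an outside frame. Some eyes may lack one fluid type at baseline, since Section 4 asks for intraretinal or subretinal edema, so the usable number per type may be below 5. Both points stand.

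What the reply leaves open is the secondary endpoint itself. If CST is its measure, it duplicates the primary endpoint. If the presence reading is its measure, it cannot register a graded change.

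**Conclusion.** The point holds in a narrow form. One secondary endpoint, change in intraretinal and subretinal edema, has no stated metric. The only measure in Section 10 that separates the two fluid types is a presence reading, on which partial clearing and worsening are both recorded as unchanged. CST is continuous but cannot attribute a change to either type.

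That loss follows from the scale and needs no assumption. Its frequency does: the 13% to 34% of eyes with an unrecorded large fall, and the 2% to 25% with an unrecorded increase, rest on 50% drying, a capped normal distribution, an SD of 0.5 to 1.5 of baseline, and fluid of that type in every eye at baseline.

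A reader might infer a power gain from the graded measure in every setting. Step 4 of the working shows one where there is none, and no test or level is specified in any case. The argument for change is descriptive: five per-eye values say more than a count from 0 to 5. Severity is minor.

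**What to change.** Keep the presence reading and add to Section 10.1: *For each study eye, maximum subretinal fluid height and maximum intraretinal fluid (cyst) height will be measured in µm by caliper on the Heidelberg OCT at baseline and each visit, entered as 0 if that fluid type is absent. Values will be listed per eye, and the change from baseline to Month 3 will be summarized for each fluid type by mean, SD, median, minimum and maximum.*

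Then reconcile the Response Measures, the secondary endpoint list and Section 10.1, stating which measure defines the secondary fluid endpoint. Caliper height is one workable choice. The documents do not favor a particular graded metric, and another could serve if it is named in advance.

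The cost is one added sentence or two, a numeric field for each fluid type, caliper work on up to 5 eyes × 6 visits in Table 1 = 30 study-eye scans, and some measurement error. No scan or visit is added, because Heidelberg OCT is scheduled at all six visits and a manual reading is already planned.
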